5.6.4. Electrocardiograms

A single 12-lead ECG will be obtained on all subjects at screening. A listing of clinical ECGs -- comprising QT, heart rate, QTcB, QTcF, PR, RR and QRS – will be presented.

5.6.5. Physical Examination

Physical examination assessments will be listed and summarized by treatment in accordance with the sponsor reporting standards. Baseline is as defined in [Section 2.4](#).

5.6.6. Neurological Examination

Neurological examination will be listed and summarized by treatment. Baseline is as defined in [Section 2.4](#).

6. INTERIM ANALYSES

Not applicable.

8. APPENDICES

Appendix 1. Summary of Efficacy Analyses

Endpoint	Analysis Type	Population	Data Inclusion and Rules for Handling Intercurrent Events and Missing Data	Analysis Model
Change from baseline to Month 24 in mean standing height	Summary	FAS	Separately for observed data and imputed data.	N/A
	Main analysis	FAS	All data collected will be included regardless of intercurrent events. Missing data will not be imputed.	MMRM with terms time,dose, gender & age
	Sensitivity/supplementary analysis	PPAS	All data collected will be included regardless of intercurrent events. Missing data will not be imputed.	MMRM with terms time,dose, gender & age
Change from baseline to Month 12 in mean arm span-height difference	Summary	FAS	Separately for observed data and imputed data.	N/A
	Main analysis	FAS	All data collected will be included regardless of intercurrent events. Missing data will be not be imputed.	MMRM with terms time,dose, gender & age
	Sensitivity/supplementary analysis	PPAS	All data collected will be included regardless of intercurrent events. Missing data will not be imputed.	MMRM with terms time,dose, gender & age

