#### **9.3.3. Secondary Endpoint(s)/Estimand(s) Analysis**

The secondary efficacy endpoint of change from baseline of the difference of arm span to height difference at 24 months will be analyzed using an ANOVA model comprising terms for recifercept dose groups. Change from baseline estimates for height and their corresponding 80% confidence intervals will be provided via least-square means. The population for the primary analysis will be based on the FAS.

Additional safety endpoints (laboratory values, physical examination, vital signs and immunogenicity) will be analyzed as change from baseline by dose group.

CCI [REDACTED]

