1.1.2. Secondary Estimand(s)

The secondary efficacy estimand comprises the following 4 attributes:

- Population: Patients with achondroplasia, as defined by inclusion/exclusion criteria;
- Variable: Change from baseline to 24 months in the difference between arm span (cm) and standing height (cm);
- Intercurrent event: Withdrawal and all events leading to missing data will be excluded from efficacy analysis and will not have their data imputed;
- Population-level summary: Mean change-from-baseline of arm span/standing height difference at 24 months adjusted for age and gender.

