5.2. Secondary Endpoint(s)

5.2.1. Arm span to height/length difference

5.2.1.1. Main Analysis

- Estimand strategy: Hypothetical ([Section 1.1.1](#)).
- Analysis set: FAS ([Section 3](#)).

- Analysis methodology: Change from baseline for Arm span to height/length difference will be analyzed MMRM including data from Months 3-24 with gender and whether a subject has switched doses of recifercept as covariates, subject (and/or time) as a random effect and an unstructured covariance matrix ([Section 4.2.1](#)).
- Intercurrent events and missing data: Data after study drug discontinuation and rescue will be excluded; intermediate missing values will not be imputed.
- The sample size, mean, standard deviation, median, minimum, and maximum at the baseline and postbaseline visits for observed standing height and change from baseline will be presented for each treatment arm.

The least-squares (LS) means, the 95% confidence interval for the LS means, the difference between the LS means for each pair of treatment groups, and the corresponding 95% confidence interval will be presented for change from baseline in standing height for all postbaseline visits.

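### SAP Appendix 1 sets the arm span-height difference at Month 12, while the SAP's own estimand and the protocol set it at Month 24

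*SAP*

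**What the plan says.** The secondary estimand in SAP 1.1.2 gives 24 months twice: once in the variable and once in the population-level summary, "Mean change-from-baseline of arm span/standing height difference at 24 months adjusted for age and gender". Protocol 9.3.3 agrees and describes the analysed quantity as "change from baseline of the difference of arm span to height difference at 24 months".

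SAP 5.2.1.1 specifies the main analysis as "MMRM including data from Months 3-24 with gender and whether a subject has switched doses of recifercept as covariates". It names no single visit as the endpoint. Its sentence on LS means and confidence intervals refers to "change from baseline in standing height for all postbaseline visits", which is the primary variable and not this one.

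SAP Appendix 1 then lists the endpoint as "Change from baseline to Month 12 in mean arm span-height difference" and attaches the summary, main and per-protocol analyses to that label. The standing-height row of the same table is at Month 24.

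**The concern.** The time point is part of the endpoint's definition. Two analysts who took it from different parts of the SAP would report two different quantities under the same name: growth in the arm span difference over the first year of the extension, or over both years.

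This is the only secondary efficacy endpoint with its own model. Those in SAP 5.2.2 to 5.2.10 are summarised descriptively. The study is open label, and protocol 9.4 lets the sponsor review data while it runs, so the endpoint visit should be fixed in one place and stated the same way everywhere.

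**Working it through.** **1. The places side by side**

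| Place | Time point for the arm span-height difference |
|---|---|
| SAP 1.1.2, variable | 24 months |
| SAP 1.1.2, population-level summary | 24 months |
| Protocol 9.3.3 | 24 months |
| SAP 5.2.1.1 | Months 3 to 24 in the model, no endpoint visit named |
| SAP Appendix 1, arm span row | Month 12 |
| SAP Appendix 1, standing-height row (for comparison) | Month 24 |

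Month 12 appears once, and every other place that names a visit says Month 24.

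**2. Can visit windows explain it?** From SAP Appendix 2.1, Month 12 is Day 361 (window 346 to 375) and Month 24 is Day 721 (window 706 to 735). The targets are 721 − 361 = 360 days apart, and the windows are separated by 706 − 375 = 331 days. They cannot be read as the same visit.

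**3. How far apart are the two definitions?** From Day 1, Month 12 is 361 − 1 = 360 days and Month 24 is 721 − 1 = 720 days, so 360/720 = 50% of the extension period. Anthropometry is 3-monthly (protocol 8.1.1), which gives 24/3 = 8 scheduled post-baseline measurements. Four fall by Month 12 and four after it (Months 15, 18, 21 and 24). These figures measure the distance between two labels, not data lost. They also describe the extension only, since participants enter already treated in C4181005.

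**4. Does any passage resolve it?** Protocol section 9 and SAP section 1 allow the SAP to modify the protocol. That does not help, because the conflict lies inside the SAP. SAP section 6 has no interim analysis that would need Month 12, and the SAP version table records no change.

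**5. Would the plan yield a Month 24 estimate anyway?** SAP 4.2.1 includes a treatment-by-visit interaction and asks for LS means at each visit, so under that general rule it would. Two details work against it:

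- The LS-means sentence in 5.2.1.1 names the wrong variable, as shown above.
- The Appendix 4 code, which is stated to serve both endpoints, has dose, month, gender and age but no dose-by-month term, and requests LS means by dose only. Assuming all eight visits are levels of month with equal weight, the result averages over visits with mean time (3 + 6 + 9 + 12 + 15 + 18 + 21 + 24)/8 = 108/8 = 13.5 months. That is neither a Month 12 nor a Month 24 estimate, and the dose differences are the same at every visit by construction. The model terms listed in Appendix 1 also omit the interaction.

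No sample size, power or alpha is attached to this endpoint, so there is no planned figure to reproduce.

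**The case against.** The strongest reply is that this is an editorial slip in a summary table. The estimand and the protocol both pre-specify 24 months, the neighbouring row says Month 24, and one outlying row should not override them. The SAP shows other signs of text carried over from another study: its version date of 21 Dec 2020 precedes the original protocol of 02 August 2021, and Appendix 2.1 has Day 4, 8 and 15 windows that this study's schedule lacks. Carry-over is an inference, but a plausible one. It explains the row without making it correct.

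The reply is right to limit the consequence. Three stronger readings are tempting, and the documents do not support them:

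- A reader might infer that following Appendix 1 drops the second year. It does not. The row includes all collected data and has time as a model term, and 5.2.1.1 uses Months 3 to 24. The two places differ on data after discontinuation, which is a separate matter, but neither stops at Month 12.
- A reader might infer that Appendix 1 governs the programming. No passage says so; its title presents it as a summary.
- A reader might infer that the ambiguity opens the way to selective claims of success. SAP 4.1 states no hypotheses, so there is no decision rule to exploit. SAP 4.2.1 plans estimates at every visit, so both time points would be visible even after correction.

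What survives is the internal conflict over which visit is the endpoint.

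**Conclusion.** The contradiction is real and can be verified from the SAP alone. Appendix 1 assigns Month 12 to an endpoint that SAP 1.1.2 and protocol 9.3.3 assign to Month 24, and nothing explains the difference. Taken literally, that row targets a different estimand.

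Its size is modest. The two visits are 360 days apart, or half of the extension period, but no measurement is lost, no test or error rate is affected, and the primary endpoint is untouched. The conclusion assumes that the estimand and the protocol state the intended time point, which their agreement and the Month 24 primary row support. The correction should be made before the final analysis, because no other part of the SAP clearly delivers a Month 24 estimate of this endpoint: the reporting sentence in 5.2.1.1 names another variable and the supplied code averages over visits.

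**What to change.** - In SAP Appendix 1, change the arm span row from Month 12 to Month 24. If Month 12 is wanted, add it as a separate, descriptive time point.
- In SAP 5.2.1.1, make the LS-means sentence name the arm span-height difference instead of standing height, and identify Month 24 as the endpoint visit.
- In SAP Appendix 4, add the dose-by-month term that 4.2.1 already specifies, and request LS means by dose at Month 24. List the same term in the Appendix 1 model column.

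The cost is a few lines of SAP text and code. Visits, data collection and the protocol text on the time point stay as they are.

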Appendix 2. Data Derivation Details

Appendix 2.1. Definition and Use of Visit Windows in Reporting

Visit Label	Target Day	Start Day	End Day
Day 1	Day 1	Day 1	Day 1
Day 4	Day 4	Day 2	Day 6
Day 8	Day 8	Day 7	Day 9
Day 15	Day 15	Day 10	Day 19
Day 29	Day 29	Day 20	Day 39
Month 2	Day 61	Day 40	Day 75
Month 3	Day 91	Day 76	Day 105
Month 4	Day 121	Day 106	Day 135
Month 5	Day 151	Day 136	Day 165
Month 6	Day 181	Day 166	Day 195
Month 7	Day 211	Day 196	Day 225
Month 8	Day 241	Day 226	Day 255
Month 9	Day 271	Day 256	Day 285
Month 10	Day 301	Day 286	Day 315
Month 11	Day 331	Day 316	Day 345
Month 12	Day 361	Day 346	Day 375
Month 13	Day 391	Day 376	Day 405
Month 14	Day 421	Day 406	Day 435
Month 15	Day 451	Day 436	Day 465
Month 16	Day 481	Day 466	Day 495
Month 17	Day 511	Day 496	Day 525
Month 18	Day 541	Day 526	Day 555
Month 19	Day 571	Day 556	Day 585
Month 20	Day 601	Day 586	Day 615
Month 21	Day 631	Day 616	Day 645

Month 22	Day 661	Day 646	Day 675
Month 23	Day 691	Day 676	Day 705
Month 24	Day 721	Day 706	Day 735

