## 1.2. Schema

### 1.3. Schedule of Activities

The SoA table provides an overview of the protocol visits and procedures. Refer to the [STUDY ASSESSMENTS AND PROCEDURES](#) section of the protocol for detailed information on each procedure and assessment required for compliance with the protocol.

The investigator may schedule visits (unplanned visits) in addition to those listed in the SoA table, in order to conduct evaluations or assessments required to protect the well-being of the participant.

	Enrollment	M1 b	M2 b	M3	M4 b	M5 b	M6	M7 b	M8 b	M9	M10 b	M11 b	M12	M13 b	M14 b	M15	M16 b	M17 b	M18	M19 b	M20 b	M21	M22 b	M23 b	M24	Early Term/Discon.	Follow-up	
Visit Identifier	1	2	3	4	5	6	7	8	9	10	11	12	13	14	15	16	17	18	19	20	21	22	23	24	25	26	27	
Days Relative to Day 1 a	1	29	61	91	121	151	181	211	241	271	301	331	361	391	421	451	481	511	541	571	601	631	661	691	721			
Visit Window (Days)	±7	±7	±7	±7	±7	±7	±7	±7	±7	±7	±7	±7	±7	±7	±7	±7	±7	±7	±7	±7	±7	±7	±7	±7	±7	±7	±7	
Informed consent/assent	X																											
Demography c	X																											
Medical history	X																											
Pregnancy test c	X	X	X	X	X	X	X	X	X	X	X	X	X	X	X	X	X	X	X	X	X	X	X	X	X	X	X	
Contraception check c	X	X	X	X	X	X	X	X	X	X	X	X	X	X	X	X	X	X	X	X	X	X	X	X	X	X	X	
Inclusion/Exclusion Check	X																											
Randomisation	X																											
Physical examination d				X			X			X			X			X			X			X			X	X		
Neurological examination				X			X			X			X			X			X			X			X	X		
Weight				X			X			X			X			X			X			X			X	X		
Vital signs				X			X			X			X			X			X			X			X	X		
Hematology				X			X			X			X			X			X			X			X	X		
Blood chemistry				X			X			X			X			X			X			X			X	X		
Study intervention dispensing	X	X	X	X	X	X	X	X	X	X	X	X	X	X	X	X	X	X	X	X	X	X	X	X	X	X		
Study intervention administration	X	→	→	→	→	→	→	→	→	→	→	→	→	→	→	→	→	→	→	→	→	→	→	→	→			
Dosing diary	X	→	→	→	→	→	→	→	→	→	→	→	→	→	→	→	→	→	→	→	→	→	→	→	→			
Anthropometry				X			X			X			X			X			X			X			X	X		

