## 7.2. Participant Discontinuation/Withdrawal from the Study

A participant may withdraw from the study at any time at his/her own request. Reasons for discontinuation from the study include the following:

- Refused further study procedures;
- Lost to follow-up;
- Death;
- Study terminated by sponsor.

At the time of discontinuing from the study, if possible, an early discontinuation visit should be conducted. See the [SoA](#) for assessments to be collected at the time of study discontinuation and follow-up and for any further evaluations that need to be completed.

The early discontinuation visit applies only to participants who are enrolled/randomized and then are prematurely withdrawn from the study. Participants should be questioned regarding their reason for withdrawal.

The participant will be permanently discontinued from the study intervention and the study at that time.

If a participant withdraws from the study, he/she may request destruction of any remaining samples taken and not tested, and the investigator must document any such requests in the site study records and notify the sponsor accordingly.

If the participant withdraws from the study and also withdraws consent (see [Section 7.2.1](#) for disclosure of future information, no further evaluations should be performed and no additional data should be collected. The sponsor may retain and continue to use any data collected before such withdrawal of consent.

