## **8.1. Efficacy Assessments**

### **8.1.1. Anthropometric Measurements**

Anthropometric measurements for height and proportionality will be performed and reported in the eCRF. Anthropometric measurements will be performed according to a trial-specific Anthropometric Measurement Manual, which will be provided to the investigational sites. This manual will contain a detailed description on the following:

- Which measurements to perform.
- The tools/instruments to be used.
- Standard procedure for performing these measurements.

The measurements to be taken on a 3-monthly basis are:

- Standing height (length for participants <2 years of age);
- Sitting height (crown-rump length for participants <2 years of age);
- Knee height;
- Head circumference;
- Arm span;
- Body weight;
- Elbow extension angle;
- Cranial dimensions (occipito-frontal, occipito-nasal distances).

Waist and chest circumference will be measured at baseline and at final visit.

Anthropometric data will only be collected by appropriately trained individuals at the trial site and in accordance with the anthropometric measurement manual. All sites will follow a consistent, structured and documented training program. This will occur prior to trial start, through regular refresher training and at targeted retraining based on analysis of measurement data consistency at the site.

Sites will be required to make all efforts to have the same anthropometrist at each visit for each participant (longitudinal consistency) and between participants (cross-sectional consistency). As well as following the specific procedures for measurement laid out in the measurement manual, sites will be provided with the same (or exactly equivalent) equipment across all sites and will follow the specific calibration procedures.

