#### **10.7.7. Efficacy Assessments**

Anthropometric measurements cannot be undertaken in the participant's home. Administration of PRO/ObsRO and blood draws may be undertaken by home health teams.

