1.2. Study Design

This is a Phase 2 open label extension study to assess the long-term safety, tolerability, PK and efficacy of recifercept.

Approximately 63 children from the Phase 2 C4181005 study will be offered to participate who, in the opinion of the investigator, continue to have a positive risk:benefit profile. Participants will be children diagnosed with achondroplasia aged $\geq 15\text{m}$ - ≤ 12 years (inclusive). All participants will continue to receive 1 of 3 doses of recifercept (1 mg/kg QW, 2 mg/kg BIW or 1.5 mg/kg QD) until a therapeutic dose is identified for up to 24 months.

Enrollment of participants will follow their completion of the C4181005 Phase 2 study and only be offered to those who, in the opinion of the investigator, continue to have a positive risk: benefit profile. PK and immunogenicity samples will be collected to assess long-term safety of recifercept.

Once a final therapeutic dose has been identified, the Pfizer IRC may decide to extend the study treatment duration and data collection (including final adult height) period beyond 24 months. Any significant changes to the protocol will be made via substantial protocol amendment.

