4.1. Hypotheses and Decision Rules

There are no statistical hypotheses for this protocol.

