4.2.1. Analyses for Longitudinal Continuous Endpoints

Mixed-effect, repeated measures (MMRM) models will be used. The fixed effects of treatment, visit, treatment-by-visit interaction, age and gender will be included. Visit will be modeled as a categorical covariate. (If the model does not converge then Visit will be modeled as a continuous covariate.) Unstructured covariance matrix will be assumed for the model errors. Compound symmetry covariance matrix will be used if the model with unstructured variance covariance doesn't converge.

When modeling the change from baseline values, the variable for visit will start with the first post-baseline visit. At each visit, estimates of least square mean (LSM) values and the LSM differences between treatment groups will be derived from the model. The corresponding p-values and 95% confidence intervals will also be derived from the model.

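### The SAP labels 3-monthly heights with 30-day monthly windows, so early-termination and very late heights can become near-empty visit levels in the primary model

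*SAP*

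**What the plan says.** **Timing of heights.** Protocol Section 8.1.1 lists standing height under "The measurements to be taken on a 3-monthly basis are". The Schedule of Activities marks anthropometry at Months 3, 6, 9, 12, 15, 18, 21 and 24 and at the early-termination visit. All visits have a ±7-day allowance. The months in between are telephone contacts.

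**Heights at other times.** Protocol Section 7.2 says that, if possible, "an early discontinuation visit should be conducted" when a child leaves the study. That visit has no fixed day. The Schedule of Activities also allows unplanned visits. Under the public-emergency measures, Protocol Section 10.7.7 says "Anthropometric measurements cannot be undertaken in the" participant's home, so a height due while the clinic is closed has to wait or be missed.

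**Labels.** SAP Appendix 2.1 runs without gaps from Day 1 to Day 735. From Month 3 to Month 24 each month has its own 30-day window, for example "Month 7 Day 211 Day 196 Day 225". The table also has Day 4, Day 8 and Day 15 windows that match no visit in the Schedule of Activities.

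**Model.** SAP Section 5.1.1.1 analyses height growth with an MMRM on data from Months 3 to 24, not restricted to quarterly months. It asks for LS means and pairwise dose differences at every postbaseline visit. SAP Section 4.2.1 adds a treatment-by-visit interaction and an unstructured covariance, and states that "Visit will be modeled as a categorical covariate". If the model does not converge, visit becomes continuous; if the unstructured covariance fails, compound symmetry replaces it.

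I found no rule that moves an off-quarter height to a quarterly visit, none that discards it, and none that chooses between two heights in one window.

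**The concern.** The label decides which visit level a height belongs to in the model. Followed literally, the table turns a height taken on Day 210 into a Month 7 observation, although no height is scheduled in Month 7. With visit categorical, Month 7 becomes a level of its own, probably holding one child in one dose group. The Month 7 means for the other two dose groups are then inestimable under the interaction model, and so are the pairwise differences that Section 5.1.1.1 asks for.

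The larger risk is to the model as a whole. A handful of stray labels adds variances and covariances that the data cannot identify. That could trigger a fallback, so the form of the primary analysis could be settled by a few irregular visits. These heights also come largely from children who leave early, where the handling of incomplete data needs to be settled in advance.

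**Working it through.** The documents give no figure on this point, so there is none to reproduce.

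**Inputs.** Window table: SAP Appendix 2.1. Height visits and ±7 days: Schedule of Activities. Sample size: about 63 (SAP Section 1.2). Dropout is not stated; I assume 10% to 25%, with exits uniform over Days 76-735.

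**1. Scheduled visits.** Month 3 has target Day 91 and window Days 76-105, which is -15 to +14 days. The other quarterly windows have the same shape.
- Permitted days: 8 visits × 15 days = 120. Mislabelled: 0.
- A label changes only when a visit is at least 15 days late or at least 16 days early.
- Share of late days that change label (Months 3 to 21): delays of 1-14 days, 0/14 = 0%; 1-21 days, 7/21 = 33%; 1-30 days, 16/30 = 53%.
- Month 24: 721 + 15 = Day 736, which is past the last window and has no label.

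**2. Early-termination days.**
- Days 76-735: 735 - 76 + 1 = 660.
- In a quarterly window: 8 × 30 = 240 (36%).
- Off-grid: 660 - 240 = 420, and 420/660 = 63.6%.
- Other ranges: Days 2-735, 494/734 = 67.3%; Days 76-721, 420/646 = 65.0%.

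**3. Number of heights affected.**
- 10% dropout: 63 × 0.10 × 0.636 = 4.0.
- 25% dropout: 63 × 0.25 × 0.636 = 10.0.
- As a share of postbaseline heights, taking leavers to miss half their visits on average: 4.0/(63 × 8 × 0.95) = 0.8% and 10.0/(63 × 8 × 0.875) = 2.3%.
- Spread over the 14 off-quarter months: 4.0/14 = 0.3 and 10.0/14 = 0.7 per month, so an occupied level would usually hold one or two children.

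**4. Size of the model.** An unstructured covariance on v visits has v(v + 1)/2 parameters.

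| Visit levels | Parameters |
|---|---|
| 8 (quarterly only) | 8 × 9/2 = 36 |
| 8 + 4 = 12 | 12 × 13/2 = 78 |
| 8 + 10 = 18 | 18 × 19/2 = 171 |

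The last two rows are upper limits for 4 and 10 stray heights, each in a different month. A child has at most one early-termination height, so no child supplies two of these extra levels. With 4 extra levels, 4 × 3/2 = 6 covariances are seen in no child; with 10, 10 × 9/2 = 45.

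**5. Effect of 90-day windows.**
- Off-grid days in Days 76-735 fall from 420 to 0. Over Days 2-735 they fall from 494 to 44 (Days 2-45).
- The off-grid days form 7 gaps of 60 days, for example Days 196-255. The first 30 days of each gap (196-225) share a proposed window with the completed Month 6 visit; the other 30 (226-255) fall in the Month 9 window.
- A closest-to-target rule therefore normally keeps about 210/420 = half of these heights: 4.0 × 0.5 = 2 to 10.0 × 0.5 = 5.

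**The case against.** Much can be said for leaving the table alone. Monthly windows suit a study with monthly contacts, and no height taken within the protocol's allowance is mislabelled. The affected heights are about 1% to 2% of the total. The SAP states that "There are no statistical hypotheses for this protocol" and gives fallbacks for non-convergence. The Day 4, 8 and 15 windows do no harm to height, since none is scheduled then. The Appendix 4 code has no dose-by-month term, so inestimable dose-by-visit means follow from the text of Sections 4.2.1 and 5.1.1.1, not from the code.

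Whether early-termination heights count at all is a separate question. Section 5.1.1.1 excludes data after study drug discontinuation, and Section 1.1.1 excludes withdrawals from the efficacy analysis. Appendix 1 includes everything collected. If the exclusion governs, heights taken after the drug is stopped are out under any window table.

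These points stand, and they limit the size of the problem. They do not remove it: the ±7 days cannot control when a child leaves, a fallback set off by stray labels still changes the primary model, and the unlabelled heights after Day 735 are at the primary time point.

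Three stronger readings are tempting, and the documents do not support them:
- That 64% of visits or heights are affected, delayed ones included. It is a share of calendar days under uniform exits. For delays the share is 0% up to 14 days.
- That off-quarter heights drop out of the model. No text discards them; as written, those in Months 3 to 24 enter under their own month label.
- That the covariance grows to 253 parameters. That needs all 22 monthly levels occupied (22 × 23/2), and 4 to 10 stray heights cannot fill the 14 off-quarter ones.

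**Conclusion.** The point holds as a stated labelling rule that does not fit the measurement schedule. It leaves routine visits untouched. It affects early-termination heights, heights at least about 15 days off target, and Month 24 heights after Day 735. On an assumed 10% to 25% dropout with uniform exits, about 4 to 10 early-termination heights fall off the grid (2 to 12 if dropout is 5% to 30%). At most these raise the visit levels from 8 to between 12 and 18, and the unstructured covariance from 36 parameters to between 78 and 171. Non-convergence is possible, not certain. The count also presumes that early-termination heights are analysed, which the SAP leaves contradictory. Few observations are involved, but they can determine which primary model is fitted, so the change should be made.

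**What to change.** 1. For assessments made every 3 months, replace the monthly windows with contiguous windows of about 90 days centred on the quarterly targets: Month 3, Days 46-135; Month 6, Days 136-225; and so on. Bound Month 24, for example Days 676-765.
2. When a window holds two values, keep the one closest to target. An early-termination height is then normally used only when its window has no scheduled height, which is about half of them.
3. Compute expected growth from the child's actual age on the measurement date, interpolating the reference to that age. Appendix 2.2 now builds reference means only at 6-month steps, so that derivation and its code need the change too.
4. Delete the Day 4, 8 and 15 windows.
5. Reconcile SAP Section 5.1.1.1 with Appendix 1 on whether heights after drug discontinuation count.

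**Cost.** One SAP revision before analysis, with no new data. The downside is that heights up to about 45 days from target share a label. The actual-age denominator corrects this for the growth ratio, but not for outcomes in centimetres such as the arm span-height difference or change in standing height. Add a narrower-window sensitivity analysis for those.
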